#### **10. DRUG INFORMATION**

#### 10.1 Venetoclax (ABT-199)

#### **10.1.1 Pharmacological Properties and FDA-Approved Indication**

Venetoclax is a BCL-2 inhibitor indicated for the treatment of patients with chronic lymphocytic leukemia (CLL) with 17p deletion, as detected by an FDA approved test, who have received at least one prior therapy.

#### **10.1.2 How Supplied**

AbbVie will supply Venetoclax at no charge to subjects participating in this clinical trial.

Drug Packaging configurations: 10mg 16 tablets/card, 50mg 1×8 blister card, 100mg 1×8 blister cards, 100mg 2×8 blister cards, 100mg 120 count bottles.

Venetoclax 10 mg film-coated tablets are round, biconvex shaped, and pale yellow.

Venetoclax 50 mg film-coated tablets are oblong, biconvex shaped, and beige.

Venetoclax 100 mg film-coated tablets are oblong, biconvex shaped, and pale yellow.

#### **10.1.3 Preparation**

Venetoclax is taken 1 time a day with a meal and water at about the same time each day.

#### **10.1.4 Storage and Stability**

Store at 15 to 25 degrees C (59-77 degrees F)

#### **10.1.5 Handling and Disposal**

Subjects will be instructed to do the following when given Venetoclax to take home:

- Keep Venetoclax in a safe place, away from other family members' medications and away from any food or drinks.
- Store the medication at room temperature in a dry location avoid storing medication in the bathroom.
- Store Venetoclax in its original container, which may be a blister pack
- Keep the medication out of reach from children and pets.
- Return damaged or unused Venetoclax to the study physician

#### 10.1.6 Dispensing

Venetoclax must be dispensed only from official study sites and to eligible subjects under the supervision of the site investigator. Venetoclax should be stored in a secure area according to local regulations. It is the responsibility of the site investigator to ensure that study drug is only dispensed to subjects.

#### **10.1.7** Adverse events

The most common adverse reactions ( $\geq 20\%$ ) in clinical trials were neutropenia, diarrhea, nausea, anemia, upper respiratory tract infection, thrombocytopenia, and fatigue. Warnings include Tumor Lysis Syndrome and neutropenia. Refer to the package insert for a comprehensive list of adverse events.

Please refer to the latest version of the prescribing information which can be found at http://www.accessdata.fda.gov/scripts/cder/drugsatfda/, and/or on the manufacturer's website.

#### **10.2** Gemtuzumab Ozogamicin (MYLOTARGTM)

#### **10.2.1** Pharmacological Properties and FDA-Approved Indication

Gemtuzumab Ozogamicin is a CD33-directed antibody-drug conjugate indicated for:

- treatment of newly-diagnosed CD33-positive acute myeloid leukemia (AML) in adults
- treatment of relapsed or refractory CD33-positive AML in adults and in pediatric patients 2 years and older

#### **10.2.2 How Supplied**

Pfizer will supply Gemtuzumab Ozogamicin at no charge to subjects participating in this clinical trial.

MYLOTARG (Gemtuzumab Ozogamicin) for Injection is a white to off-white lyophilized cake or powder supplied in a carton (NDC 0008-4510-01) containing one 4.5 mg single-dose vial.

#### **10.2.3 Preparation**

Use appropriate aseptic technique for the reconstitution and dilution procedures. Protect the reconstituted and diluted MYLOTARG solution from light.

# **Reconstitution**

- MYLOTARG is a cytotoxic drug. Follow applicable special handling and disposal procedures.1
- Calculate the dose (mg) and number of vials of MYLOTARG required.
- Prior to reconstitution, allow drug product vials to reach ambient temperature for approximately 5 minutes.
- Reconstitute each vial with 5 mL of Sterile Water for Injection, USP to obtain a concentration of 1 mg/mL of MYLOTARG that delivers 4.5 mL (4.5 mg).
- Gently swirl the vial to aid dissolution. DO NOT SHAKE.
- Inspect the reconstituted solution for particulates and discoloration. The reconstituted solution may contain small white to off-white, opaque to translucent, and amorphous to fiber-like particles.
- MYLOTARG contains no bacteriostatic preservatives.
- Use reconstituted solution immediately or after being refrigerated at 2–8°C (36–46°F) for up to 1 hour. Protect from light. Do not freeze.

# Dilution

• Calculate the required volume of the reconstituted solution needed to obtain the appropriate dose according to patient body surface area. Withdraw this amount from the vial(s) using a syringe. Protect from light. Discard any unused reconstituted solution left in the vial.

# Doses must be mixed to a concentration between 0.075 mg/mL to 0.234 mg/mL according to the following instructions:

- Doses less than 3.9 mg must be prepared for administration by syringe. Add the reconstituted MYLOTARG solution to a syringe with 0.9% Sodium Chloride Injection to a final concentration between 0.075 mg/mL to 0.234 mg/mL. PROTECT FROM LIGHT.
- Doses greater than or equal to 3.9 mg are to be diluted in a syringe or an IV bag in an appropriate volume of 0.9% Sodium Chloride Injection to ensure a final concentration between 0.075 mg/mL to 0.234 mg/mL. PROTECT FROM LIGHT.
- Gently invert the infusion container to mix the diluted solution. Do not shake.
- Following dilution with 0.9% Sodium Chloride Injection, MYLOTARG solution should be infused immediately. If not used immediately, store at room temperature (15–25°C; 59–77°F) for up to 6 hours, which includes the 2-hour infusion time and 1-hour, if needed, to allow the refrigerated diluted solution to equilibrate to room temperature. The diluted solution can be refrigerated at 2–8°C (36–46°F) for up to 12 hours which includes up to 1-hour in the vial post-reconstitution. Protect from light and do not freeze.

# Administration

- Use an in-line 0.2 micron polyethersulfone (PES) filter for infusion of MYLOTARG.
- Protect the intravenous bag from light using a light-blocking cover during infusion. The infusion line does not need to be protected from light.
- Infuse the diluted solution over 2 hours.
- Do not mix MYLOTARG with, or administer as an infusion with, other medicinal products.

# 10.2.4 Storage and Stability

Refrigerate (2–8°C; 36–46°F) MYLOTARG vials and store in the original carton to protect from light. Do not freeze.

# **10.2.5 Handling and Disposal**

MYLOTARG is a cytotoxic drug. Follow applicable special handling and disposal procedure.

# 10.2.6 Dispensing

MYLOTARG must be dispensed only from official study sites and to eligible subjects under the supervision of the site investigator. MYLOTARG should be stored in a secure area according to local regulations. It is the responsibility of the site investigator to ensure that study drug is only dispensed to study subjects.

#### **10.2.7** Adverse events

The most common adverse reactions (greater than 15%) in clinical trials were hemorrhage, infection, fever, nausea, vomiting, constipation, headache, increased AST, increased ALT, rash, and mucositis. Warnings include infusion-related reactions and hemorrhage. Refer to the package insert for a comprehensive list of adverse events.

Please refer to the latest version of the prescribing information that can be found at http://www.accessdata.fda.gov/scripts/cder/drugsatfda/, and/or on the manufacturer's website.

# 11. ADVERSE EVENTS

#### **11.1 Definitions**

#### 11.1.1 Adverse Event (AE)

An AE is any untoward medical occurrence whether or not considered related to the study drug that appears to change in intensity during the course of the study. The following are examples of AEs:

- Unintended or unfavorable sign or symptom
- A disease temporally associated with participation in the protocol
- An intercurrent illness or injury that impairs the well-being of the subject

Abnormal laboratory values or diagnostic test results constitute AEs only if they induce clinical signs or symptoms or require treatment or further diagnostic tests

Hospitalization for elective surgery or routine clinical procedures that are not the result of an AE (e.g., surgical insertion of central line) should not be recorded as an AE.

Disease progression should not be recorded as an AE, unless it is attributable to the study regimen by the site investigator.

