# 5.2 Definition of Dose-limiting Toxicities

Dose-limiting toxicities (DLTs) are defined as an adverse event related (possible, probable or definite) to Venetoclax and/or Gemtuzumab Ozogamicin fulfilling one of the following criteria:

 Hematologic toxicity: treatment-related grade 3 or worse neutropenia and/or thrombocytopenia due to bone marrow hypocellularity present at the end of cycle one (day 28) with an additional 28 days allowed for count recovery (i.e. present at day 56); specifically grade 3 or worse neutropenia or thrombocytopenia with the bone marrow documented to be free of leukemic infiltration. Note: patients who enter the study with grade 3 or worse cytopenias will not be evaluable for hematologic dose-limiting toxicities.

• Non-hematologic toxicity: any grade 3 or worse treatment-related toxicity occurring within the first cycle (excluding grade 3-4 infections during cycle one).

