After induction, patients demonstrating complete remission or partial remission will continue to consolidation. Patients in CRi (ANC <  $1.0 \times 10^9$ /L or platelets <  $100 \times 10^9$ /L) will stop Venetoclax for up to four weeks to allow for cytopenia recovery. If the ANC recovers to  $\ge 1.0 \times 10^9$ /L and the platelets recover to  $\ge 100 \times 10^9$ /L, consolidation will ensue. If there is not full ANC AND platelet recovery to the aforementioned levels, consolidation will be omitted, and patients will enter the maintenance phase with Venetoclax alone provided they do not have any grade 3-4 cytopenias. The previously assigned Venetoclax dose will be resumed and the maintenance rules for Venetoclax dose adjustments or discontinuation will apply (see section 6.2.2). If however patients have a grade 3-4 cytopenia despite holding Venetoclax for four weeks, they will be *removed from study* [NOTE: this applies to both induction and consolidation.]

Cycle 2: The second cycle (consolidation) will consist of GO 3 mg/m^2 IV infusion (up to one 4.5 mg vial) on days +1, and +4, in addition to daily oral administration of Venetoclax at the assigned dose. A bone marrow assessment will occur on day 28 regardless of cytopenias and those with CR, CRi, or at least a partial remission will continue onto maintenance therapy with Venetoclax alone. The previously assigned Venetoclax dose will be resumed and the maintenance rules for Venetoclax dose adjustments or discontinuation will apply (see section **6.2.2**).

After day 28, in the absence of leukemia in the BM, where there is a grade 3-4 cytopenia (thrombocytopenia or neutropenia), Venetoclax should be held for up to four weeks to allow recovery of counts to platelets  $\geq 50 \times 10^9$ /L and ANC  $\geq 1.0 \times 10^9$ /L (to allow entry into Maintenance Phase). Those who continue to have a grade 3-4 cytopenia will be taken off study.

Patients with treatment failure (see Section 9.1) will be taken off study. Please note that any patient with residual disease (with at least PR) may move onto consolidation regardless of blood counts.

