# 6.2.1 Gemtuzumab

# Table 5. Gemtuzumab Delay/Discontinuation

Event	Gemtuzumab Action
Persistent Thrombocytopenia	Discontinue if platelets do not recover to $\ge 100 \times 10^9/L$ after temporary cessation of Venetoclax for four weeks
Persistent neutropenia	Discontinue if ANC does not recover to $\ge 1.0 \times 10^9$ /L after temporary cessation of Venetoclax for four weeks
VOD	Discontinue
Total bilirubin $> 2 \times ULN$ , or AST and/or ALT $> 2.5 \times ULN$	Interrupt until recovery of total bilirubin to ≤2 times ULN and AST and/or ALT to ≤2.5 times ULN.

The scheduled dose will be omitted if there is a delay of 3-6 days between sequential infusions.

Table 6. Gemtuzumab Schedule for Interruptions

Time from missed dose	Action
<3 days	Give missed dose
3-6 days	Skip dose
≥7 days	Off study

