# 12.2 Endpoints

# **12.2.1 Definition of Primary Endpoint**

- Dose-limiting toxicity, defined as an adverse event related (possible, probably, or definite) to Venetoclax and/or Gemtuzumab fulfilling one of the following criteria:
  - Hematologic toxicity: treatment-related grade 3 or worse neutropenia and/or thrombocytopenia due to bone marrow hypocellularity present at the end of cycle one (day 28) with an additional 28 days allowed for count recovery (i.e. present at day 56); specifically grade 3 or worse neutropenia or thrombocytopenia with the bone marrow documented to be free of leukemic infiltration. Note: patients who enter the study with grade 3 or worse cytopenias will not be evaluable for hematologic dose-limiting toxicities.
  - Non-hematologic toxicity: any grade 3 or worse treatment-related toxicity occurring within the first cycle (excluding grade 3-4 infections during cycle one).

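### Under the AE definition in 11.1.1, an asymptomatic grade 3 or worse liver value in cycle 1 need not be an adverse event, so it need not be counted as a DLT

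*Combined protocol and SAP*

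**What the plan says.** Section 11.1.1 gives the recording rule for laboratory findings: "Abnormal laboratory values or diagnostic test results constitute AEs only if they induce clinical signs or symptoms or require treatment or further diagnostic tests". CTCAE grade is not a route in, and neither is interrupting or omitting a study drug.

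The DLT definition starts from an adverse event. Section 5.2 says that DLTs "are defined as an adverse event related (possible, probable or definite) to Venetoclax and/or Gemtuzumab Ozogamicin fulfilling one of the following criteria". Section 12.2.1, which defines the primary endpoint for analysis, has matching wording: "Dose-limiting toxicity, defined as an adverse event related (possible, probably, or definite) to Venetoclax and/or Gemtuzumab fulfilling one of the following criteria". Section 2.2.1 does the same.

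The criteria under that lead-in are written by grade:

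- Non-hematologic: "any grade 3 or worse treatment-related toxicity occurring within the first cycle", with grade 3-4 infections excepted. Laboratory values are neither named nor exempted.
- Hematologic: the cytopenia must persist to day 56, "specifically grade 3 or worse neutropenia or thrombocytopenia with the bone marrow documented to be free of leukemic infiltration".

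Sections 6.1.1 and 6.1.2 restate both criteria without mentioning an adverse event, but 6.1 refers the reader to 5.2 for the detailed definition.

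The protocol also acts on laboratory values directly. Above stated liver limits, the action for GO in Table 5 begins "Interrupt until recovery of total bilirubin". For counts, 5.4 says: "If however patients have a grade 3-4 cytopenia despite holding Venetoclax for four weeks, they will be" taken off the study.

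**The concern.** The primary endpoint is DLT, and the 3+3 rule turns on single patients. If a DLT must first be an AE, the AE definition decides which toxicities can reach the endpoint. Liver enzymes matter here: 10.2.7 lists increased AST and ALT among the most common GO reactions, and 1.2.1 gives hepatic toxicity as one reason the earlier GO schedule was changed.

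This is a multicenter study. If one site records a silent grade 3 ALT as an AE and another does not, the endpoint is not the same at both. The worst-grade AE tables in 12.6.3 would have the same unevenness. The error runs one way, because leaving an event out can only make a dose look better tolerated.

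**Working it through.** **1. Liver values, step by step.**

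- Section 3.1 admits patients with bilirubin up to 1.5 × ULN and AST/ALT up to 2 × ULN. Table 5 acts above 2 × ULN and 2.5 × ULN. A value that triggers Table 5 in cycle 1 is therefore a rise from the screening limits.
- Suppose the patient has no symptoms and is given no treatment for it. Table 5 calls for interruption, which is not one of the routes in 11.1.1.
- The calendar notes recommend liver tests at least three times weekly in induction. Recovery can be followed on those tests, so nothing beyond the schedule need be ordered.
- On that reading there is no AE and so no DLT, although the 5.2 criterion is met on grade, relatedness and timing.
- GO in cycle 1 is given only on days 1, 4 and 7. After day 7 no GO dose is left in that cycle to interrupt, and the non-hematologic withholding rows of Table 8 apply only to consolidation and maintenance. A later cycle 1 rise may therefore lead to no listed drug interruption at all.

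**2. Cytopenias.** The criterion itself names the count grades and the marrow finding. The AE lead-in still stands above it, and the day 28 marrow is scheduled whatever the counts, so it need not be a further test. The general rule and the specific criterion conflict in wording, and the specific one would normally govern.

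**3. The plan's own 3+3 figures (12.3).**

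- The p that solves P(0 of 3) = P(2 or more of 3) is 0.347; the plan states 0.35.
- The p that solves P(0 or 1 of 6) = 0.5 is 0.264; the plan states 0.26.
- The upper bound is 2/6 = 0.333; the plan states 0.33.

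All three reproduce.

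**4. What an omission would do.** Let p be the true DLT rate and u the share of DLT patients whose only DLT is an unrecorded laboratory value. The documents do not give u, so every value other than 0 is an assumption. The counted rate is q = p(1 − u).

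A level is cleared with 0 of 3, or with 1 of 3 followed by 0 of 3:

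P(clear) = (1 − q)³ + 3q(1 − q)² × (1 − q)³

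For p = 0.33 and u = 0: 0.67³ + 3 × 0.33 × 0.67⁵ = 0.301 + 0.134 = 0.434.

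For p = 0.33 and u = 0.25, q = 0.2475: 0.7525³ + 3 × 0.2475 × 0.7525⁵ = 0.426 + 0.179 = 0.605.

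| True rate p | u = 0 | u = 0.10 | u = 0.25 | u = 0.50 |
|---|---|---|---|---|
| 0.26 | 0.578 | 0.635 | 0.719 | 0.853 |
| 0.33 | 0.434 | 0.500 | 0.605 | 0.783 |
| 0.40 | 0.309 | 0.378 | 0.494 | 0.709 |

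Dose level 3 needs 0 or 1 of 6 even after 0 of 3. At p = 0.33 the chance of that is 0.358, 0.427, 0.540 and 0.741 for the same values of u.

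**The case against.** The strongest reply is that sensible sites would record these events anyway. Table 5 holds GO until recovery, and recovery cannot be shown without repeat tests, which a site may fairly call further diagnostic tests. The three-times-weekly schedule is only a recommendation. Table 5 lists the liver values in a column headed as events, 10.2.7 lists enzyme rises as adverse reactions, and 12.6.3 requires every dose hold to be summarized with its reason. This has weight. A reader might infer that the liver patient definitely has no AE, and the documents do not support that, because the clause can be read either way. The reply does not remove the problem, since a primary endpoint should not depend on which reading a site chooses, and a hold listed in a table is not a counted DLT.

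A reader might also infer that asymptomatic grade 3-4 cytopenias fall out of the endpoint, so that patients leave the study under 5.4 for events the protocol does not recognize. That goes too far. The hematologic criterion names the grades, and 6.1.1 repeats it without AE wording. A transfusion, G-CSF or an extra marrow would often satisfy 11.1.1 in any case. Section 11.1.2 also gives blood dyscrasias as an example of important medical events.

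Finally, the illustrated probabilities rest on assumed values of u. They show how sensitive the rule is and are not evidence that events will be lost.

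**Conclusion.** The gap is real for non-hematologic laboratory values. Under 11.1.1 and the AE lead-in of 2.2.1, 5.2 and 12.2.1, an asymptomatic grade 3 or worse AST, ALT or bilirubin rise in cycle 1 need not be counted, although the grade-based criterion would count it. For cytopenias the wording conflicts but nothing is clearly excluded.

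The direction is certain: any omission lowers the DLT count and favours escalation. The size cannot be derived from the documents. If a quarter of DLT patients were lost in this way at a true rate of 33%, the chance of clearing a level would be 61% rather than 43%. With a tenth lost it would be 50%, and with half 78%. If every site takes the wider reading, u is 0 and nothing is lost. A reader might infer that the recommended phase II dose will be too high, but that would follow only if sites took the narrow reading and such events occurred. The point should be corrected, because the repair is cheap and the decisions rest on three to six patients per level.

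**What to change.** In 11.1.1, add two recording routes. A laboratory abnormality is also an AE if it is CTCAE v5 grade 3 or worse and was not present at that grade at baseline, or if it leads to interruption, omission or discontinuation of a study drug. The grade route is needed because a rise after day 7 of cycle 1 may lead to no interruption.

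Then reconcile 11.1.1 with 2.2.1, 5.2, 6.1 and 12.2.1, so that one stated rule says whether a laboratory value meeting a DLT criterion counts as a DLT without symptoms or treatment. That choice is the sponsor's. It should be made with 6.3 in view, which ties a DLT to stopping protocol therapy, so the counting rule also affects treatment.

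The cost is a few sentences in the protocol and matching eCRF completion guidance. Sites will have more laboratory AEs to record, which the baseline clause limits. The counted DLT rate may rise somewhat, and 5.2 has no exception for transient laboratory values, so the sponsor should weigh the chance of rejecting a dose because of them.

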#### 11.1.2 Serious Adverse Event (SAE)

An SAE is an adverse event that:

• Results in death.

- Is life-threatening (defined as an event in which the subject was at risk of death at the time of the event; it does not refer to an event which hypothetically might have caused death if it were more severe)
- Requires inpatient hospitalization for >24 hours or prolongation of existing hospitalization. **NOTE:** Hospitalization for anticipated or protocol specified procedures such as administration of chemotherapy, central line insertion, metastasis interventional therapy, resection of primary tumor, or elective surgery, will not be considered serious adverse events.
- Results in persistent or significant disability/incapacity
- Is a congenital anomaly or birth defect
- Is an important medical event (defined as a medical event(s) that may not be immediately life-threatening or result in death or hospitalization but, based upon appropriate medical and scientific judgment, may jeopardize the subject or may require intervention (e.g., medical, surgical) to prevent one of the other serious outcomes listed in the definition above). Examples of such events include, but are not limited to, intensive treatment in an emergency room or at home for allergic bronchospasm; blood dyscrasias or convulsions not resulting in hospitalization; or the development of drug dependency or drug abuse.

# **11.1.3 Unexpected Adverse Event**

For this study, an AE is considered unexpected when it varies in nature, intensity or frequency from information provided in the current IB, package insert, or when it is not included in the informed consent document as a potential risk. Unexpected also refers to AEs that are mentioned in the IB as occurring with a class of drugs or are anticipated from the pharmacological properties of the drug, but are not specifically mentioned as occurring with the particular drug under investigation.

#### 11.1.4 Relatedness

AEs will be categorized according to the likelihood that they are related to the study drug(s). Specifically, they will be categorized using the following terms:

Unrelated The Adverse Event is not related to the drug(s)	
Unlikely	The Adverse Event is doubtfully related to the drug(s)
Possible	The Adverse Event may be related to the drug(s)
Probable	The Adverse Event is likely related to the drug(s)
Definite	The Adverse Event is clearly related to the drug(s)

